### 5.12 Biomarkers

Not applicable.

### 5.13 Other exploratory analysis

Not applicable.

### 5.14 Interim analysis

There was an interim analyses planned for this study when 203 patients completed 6 months of treatment or discontinued earlier. The details of statistical analysis can be found in the SAP of interim analysis. DMC recommended to continue the trial based on interim analysis.

## 6 Sample size calculation

As per the protocol amendent version dated 09-May-2019, approximately 600 subjects were planned to be enrolled to receive dabrafenib (150 mg BID) and trametinib (2 mg once daily) combination therapy for 12 months. Due to global drug supply availability, the enrollment of patients was slower than anticipated, resulting in the final sample of 556 enrolled patients in the study by the end of anticipated recruitment period. The final sample size is reasonably close to

the planned target. The impact of the reduced sample size for the interim analyses has been discussed in detail in the Interim SAP (dated 21-Nov-2019) and DMC charter (17-Jan-2020). See Section 2.8 and Appendix B respectively for details.

The sample size calculation was based on the primary variable. The protocol amendment dated provided justification for the planned sample size of 600. However the current sample size of 556 demonstrates that the study operating characteristics comply with the requirement to have a high probability (e.g. > 95%) for futility at IA if the true 12-month pyrexia event rate is > 20%, e.g., when the true pyrexia event rate is 27%, the probability is 95.5% for futility at interim analysis.

Detailed Operating characteristics are described below (see [Table 2-8](#)). For illustration, if the true 12-months pyrexia event rate is 30%, then there is a high chance (99.6%) of futility at the time of the interim, and the probability to continue the study and conclude success is lower than 0.001.

If the true pyrexia event rate is 20%, then the probability of observing a pyrexia event rate < 20% (i.e., study success for primary analysis) is 46.3%. If the true pyrexia event rate is lower (for example 18%), then there is 84.6% probability of declaring study success for primary analysis.

**Table 2-8 Operating Characteristics**

True 6 -month event rate	Probability to stop the study at IA	Probability of success at primary analysis (i.e., not stop at the IA and observe event rate < 20% at primary analysis)*
16%	0.016	0.980
17%	0.040	0.940
18%	0.086	0.846
19%	0.161	0.679
20%	0.265	0.463
21%	0.391	0.258
22%	0.528	0.115
25%	0.856	0.002
26%	0.917	<0.001
27%	0.955	<0.001
28%	0.978	<0.001
30%	0.996	<0.001

\* Probabilities are calculated based on the exact binomial distribution.

## 7 Changed to protocol specified analyses

### 7.1 Impact of COVID-19

Due to pandemic COVID in year 2020, some extra analyses will be performed outside protocol specified.

**Operational impact:** Specified protocol deviation categories will be assigned to important deviations related to COVID-19 (e.g., missing efficacy assessments and treatment interruptions) and these will be summarized and listed separately. A summary table of the COVID-19 related deviations by relationship category will be provided.

**Safety:** To help to evaluate the impact of the pandemic on safety, the incidence of COVID-19 related adverse event preferred terms will be presented incorporating (a) COVID-19 related adverse events with an onset date prior to the start of the outbreak (i.e., pre-2020, please refer the following paragraph for the definition) and (b) all COVID-19 related adverse events occurring before data cut-off. A listing of all COVID-related AEs will also be provided.

The Pre-COVID period is defined as before March 1, 2020 for Rest of the World and before Feb 23, 2020 for Italy patients. That means March 1 will play a data-cut off role. All the data before March 1 will be considered as pre-Covid period. The data from March 2, 2020 onwards will be considered as Post-Covid period.

The Post-COVID period is defined as after March 1, 2020 for Rest of the World and after Feb 23, 2020 for Italy patients.

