## 4 Study design

This is an open-label Phase IIIb study of dabrafenib in combination with trametinib in the adjuvant treatment of melanoma after complete resection. Patients with completely resected, histologically confirmed, BRAF V600E/K mutation-positive, high-risk [AJCC ed. 8 Stage IIIA (lymph node metastasis >1 mm), IIIB, IIIC or IIID] cutaneous melanoma will be screened for eligibility. The main purpose of the study is to assess whether an adapted AE-management algorithm for pyrexia (Fever (> 38 °C)), will reduce the incidence of Grade 3/4 pyrexia, hospitalization due to pyrexia and permanent treatment discontinuation due to pyrexia. The effectiveness of dabrafenib and trametinib therapy in this setting will also be assessed based on RFS and OS.

As per the protocol amendment version dated 09-May-2019, approximately 600 subjects were planned to be enrolled to receive dabrafenib (150 mg BID) and trametinib (2 mg once daily) combination therapy for 12 months. Due to global drug supply availability, the enrollment of patients was slower than anticipated, resulting in the final sample of 556 enrolled patients in the study by the end of anticipated recruitment period. The final sample size is reasonably close to the planned target.

At enrollment, subjects will be instructed on the pyrexia management algorithm (refer to protocol Section 6.5.1.1). Doses of study treatment may be modified and/or interrupted for management of toxicities associated with study treatment.

Three analyses are planned for this study.

- The interim analysis (IA) based on primary endpoint and secondary endpoint conducted when 203 subjects were dosed for 6 months (either completed 6 months of treatment or discontinued earlier). The data cut-off date was 16 August, 2019.
- The primary analysis is planned to be performed at 12 months after the last patient first visit (LPFV). The data cut-off is planned on 26th September, 2020.

[figure not shown]
- The final analysis will be performed at the end of the study defined as 24 months after LPFV.

At the time of IA, an independent data monitoring committee (IDMC) recommended to continue the trial without any changes.

This study consists of two Periods for Enrolled subjects:

- Treatment Period – subjects will receive up to 12 months of treatment (refer to the schedule as noted in protocol Table 8-1).

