## General analysis conventions

**Pooling of centers:** Unless specified otherwise, data from all study centers will be pooled for the analysis. Due to expected small number of patients enrolled at centers, no center effect will be assessed.

**Qualitative data** (e.g., gender, race, etc.) will be summarized by means of contingency tables; a missing category will be included as applicable. Percentages will be calculated using the number of patients in the relevant population as the denominator.

**Quantitative data** (e.g., age, body weight, etc.) will be summarized by appropriate descriptive statistics (i.e. mean, standard deviation, median, minimum, and maximum).

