### **On-treatment assessment/event and observation periods**

For adverse event reporting the overall observation period will be divided into three mutually exclusive segments:

1. **pre-treatment period:** from day of patient's sign informed consent to the day before first administration of study treatment.
2. **on-treatment period:** from date of first administration of study treatment to 30 days after date of last actual administration of any study treatment: dabrafenib or trametinib (including start and stop date).
3. **post-treatment period:** starting at day 31 after last administration of study treatment.

For cases where time of assessment and time of treatment start/stop is captured (e.g. ECG's laboratory assessments), the last available assessment before the treatment period start/stop date/time will be used.

If dates are incomplete in a way that clear assignment to pre-, on-, and post-treatment period cannot be made, then the respective data will be assigned to the on-treatment period. Refer to [section 5.1.1](#) for imputation rules concerning AE start and stop dates.

Safety summaries (tables, figures) include only data from the on-treatment period with the exception of baseline data which will also be summarized where appropriate (e.g. change from baseline summaries). In addition, a separate summary for death including on treatment and post treatment deaths will be provided. In particular, summary tables for adverse events (AEs) will summarize only on-treatment events, with a start date during the on-treatment period (**treatment-emergent** AEs).

However, all safety data (including those from the post-treatment period) will be listed and those collected during the pre-treatment and post-treatment period will be flagged.

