## 5.8 Safety analyses

All safety analyses will be based on safety set.

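### The planned COVID-19 adverse-event incidence divides by the whole safety set, although a substantial share of subjects had left the AE window before the outbreak, and its two cuts cannot show a pandemic effect

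*SAP*

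**What the plan says.** The Safety paragraph of SAP 7.1 sets out to evaluate the pandemic's impact on safety. Its wording is: "incidence of COVID-19 related adverse event preferred terms will be presented incorporating (a) COVID-19 related adverse events with an onset date prior". Cut (a) thus ends when the outbreak began, which is glossed as pre-2020, and cut (b) takes every COVID-19 related event up to data cut-off. A listing of these events is added. The next paragraph dates the outbreak differently: 1 March 2020, or 23 February 2020 for Italy.

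Section 7.1 gives no denominator, so the general rules of the SAP apply:

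- General analysis conventions (5.1): "Percentages will be calculated using the number of patients in the relevant population as the denominator".
- Section 5.8: "All safety analyses will be based on safety set". Section 5.2 defines that set as everyone with at least one dose.
- On-treatment periods (5.1.1): "Safety summaries (tables, figures) include only data from the on-treatment period", and that period runs "from date of first administration of study treatment to 30 days after date of last actual administration of any study treatment". Section 5.8.1 applies the same limit to AE summaries. Later events are listed and flagged only.

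On timing, SAP Section 4 says the interim analysis was "conducted when 203 subjects were dosed for 6 months (either completed 6 months of treatment or discontinued earlier"), and "The data cut-off date was 16 August, 2019". It describes slow enrolment "resulting in the final sample of 556 enrolled patients in the study by the end of anticipated recruitment period". SAP Section 2 re-runs the primary-analysis outputs for the final report, leaving out only the label-update analyses.

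**The concern.** A COVID-19 event can enter the table only if the subject still had on-treatment time once the outbreak had begun. Treatment lasts at most 12 months and much of the cohort was dosed in late 2018 and early 2019. Those subjects stay in the denominator although none of their pandemic-period events could be counted, so the percentage is diluted by a factor that the table does not show.

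The pair of cuts has a separate problem. For COVID-specific terms, (a) asks for COVID-19 events before COVID-19. For any non-specific term, (b) includes everything in (a) and covers more time. A reader who compares the two learns nothing about the pandemic.

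The pre- and post-COVID analyses elsewhere in SAP 7.1 concern the primary endpoint and pyrexia. This is the only planned AE-incidence summary that speaks to pandemic impact on safety more generally.

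**Working it through.** The documents state neither a COVID-19 AE rate nor a number at risk, so there is no figure to reproduce. The check is date arithmetic. The safety set is taken as 556, as the SAP does in its own tables.

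**Inputs**
- Interim cohort 203, cut-off 16 August 2019, total 556 (SAP 4).
- Treatment up to 12 months, then 30 days (SAP 4, 5.1.1).
- Month length: 28 days (Protocol 3) or 30.4375 days (SAP 5.1.1, Time units).
- Subjects who had started treatment: 37 by 30 November 2018 and 234 by 12 March 2019 (status lines of Protocol Amendments 1 and 2).
- Outbreak: 1 March 2020, or 23 February 2020 for Italy (SAP 7.1).

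**When does the window of the 203 close?** Those who stopped before the interim cut-off were out by 16 August + 30 days = 15 September 2019. For the 6-month completers, the latest possible dates are:

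| Month length | Latest first dose | Last dose at 12 months | Window closes |
|---|---|---|---|
| 28 days | 16 Aug 2019 − 168 d = 1 Mar 2019 | 30 Jan 2020 | 29 Feb 2020 |
| 30.4375 days | 16 Aug 2019 − 183 d = 14 Feb 2019 | 13 Feb 2020 | 14 Mar 2020 |

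With 28-day months all 203 are out before 1 March, with one day to spare. That is 203/556 = 36.5%, which leaves 353 at risk. With the SAP month some of the 203 are still in the window.

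**How many are out through planned completion alone?** Linear accrual between the two counts is an assumption: (234 − 37)/102 days = 1.93 per day.
- 28-day months, out before 1 March 2020: first dose by 1 March 2019, 37 + 1.93 × 91 ≈ 213 (38%).
- SAP months, out before 1 March 2020: first dose by 31 January 2019, 37 + 1.93 × 62 ≈ 157; 157/556 = 28.2%.
- Applying Italy's 23 February date to everyone gives 199 and 143.
- Taking pre-2020 literally (1 January 2020) gives only 97 and 41.

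**Adding early stopping.** A simulation assumed piecewise-uniform accrual through the two counts, first dose on 15 August 2018, last first dose on 26 September 2019 and uniform stopping times. None of these dates or shapes is stated in the documents. Share with no on-treatment day from 1 March 2020:

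| Stop early | 336-day treatment | 365-day treatment |
|---|---|---|
| 0% | 39% | about 28% |
| 20% | 47% | 38% |
| 37% | 54% | 46% |

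The 37% row mirrors the 63% who completed dabrafenib in the historical study (Protocol 1.1.1.6).

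**Effect on the rate.** If k subjects are out, the safety-set percentage is (556 − k)/556 of the at-risk percentage. Ten affected subjects read as 10/556 = 1.8% in the planned table. Among those at risk the figure is 10/399 = 2.5% (k = 157), 10/353 = 2.8% (k = 203) or 10/256 = 3.9% (k = 300, 54%).

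**The two cuts.** In the 336-day scenarios, 97 of 557 on-treatment patient-years (no early stopping) or 69 of 463 (37% stopping) fall after the outbreak. For a rare non-specific term with constant hazard, (b)/(a) is 557/460 = 1.21 or 463/394 = 1.18. Cut (b) would exceed (a) by 18–21% with no pandemic effect.

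**The case against.** A reader might infer that at least 203 subjects were never at risk and that the rate is understated by at least a third. The documents do not support that as a bound:

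- It needs 28-day months and the 1 March date, and the single day of slack is smaller than the ±3-day visit window in Protocol Table 8-1.
- Even with 28-day months, the latest window closes 6 days after Italy's date.
- With the SAP month, 28.2% is below a third until early stopping is added. Reaching 203 from 157 would need 46 of the other 399 (11.5%) to be more than 30 days off treatment by 1 March 2020, which is likely but not shown.

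A reader might also infer that (a) is near zero because the interim subjects had left. It is near zero because of how it is defined.

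Other objections carry some weight. The denominator is inferred from general rules, and the table shells are in a separate document. The percentage of treated subjects is the SAP's convention for AE tables and is correct as a whole-cohort proportion. The table is descriptive, and a full listing accompanies it. SAP 7.1 does not say that (a) and (b) will be compared. The COVID-19 term list is not given, so non-specific terms may not be included. Protocol 9.1.1 and 10.1.1 allow AE collection beyond 30 days, although such events would be listed and not tabulated.

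These points lower the severity but do not remove the mismatch. The stated aim is pandemic impact, and subjects not observed during the pandemic carry no information on it.

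**Conclusion.** The point holds as a minor one. Under the SAP's own rules the COVID-19 AE incidence uses the whole safety set, while a substantial share of that set could contribute no pandemic-period event. The share is about 28–54% at the 1 March 2020 date, so the at-risk rate would be roughly 1.4 to 2.2 times the reported one (1/0.72 to 1/0.46). A third or more is likely. The range rests on month length, interpolated accrual and assumed early stopping, and would be lower if the pre-2020 gloss governed.

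The defect in the cuts needs none of these assumptions: (a) is essentially empty for COVID-specific terms, and (b) contains (a) for any other. The primary endpoint and the trial's conclusion are unaffected.

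**What to change.** In the Safety paragraph of SAP 7.1:

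1. Reconcile the pre-2020 gloss with the 1 March / 23 February 2020 definition, and assign the boundary day itself to one period. The section now starts the later period the day after.
2. Report the incidence among safety-set subjects with at least one on-treatment day on or after the outbreak date for their region. Add the rate per 100 patient-years of on-treatment time from that date.
3. Keep the safety-set percentage as a second column.
4. Drop cut (a) for COVID-specific terms. For any non-specific terms, replace (a) and (b) with non-overlapping before and after periods, each with an exposure-adjusted rate.

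The cost is a wording change plus one at-risk flag and one exposure variable, both derived from dosing dates already collected. The downside for the sponsor is a less favourable reported rate.

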#### **Primary endpoint:**

To help to evaluate the impact of the COVID-19 on the primary endpoint and on overall pyrexia, the following sensitivity analyses will be performed. The summary analyses will be performed if we have 10% total sample size in each of the categories. The KM plot will be performed only if we have more than 30 patients have pyrexia event in each of the categories.

- 1) Composite rate of grade  $\frac{3}{4}$  pyrexia, hospitalization or permanent discontinue due to pyrexia by 12 months for Rest of the World (Full analysis set) Pre-Covid and post-Covid-period.
- 2) Composite rate of grade  $\frac{3}{4}$  pyrexia, hospitalization or permanent discontinue to pyrexia by 12 months for Italy (Full analysis set) with data cut-off Feb 23, 2020 vs data after February 23, 2020.
- 3) Composite rate of grade  $\frac{3}{4}$  pyrexia, hospitalization or permanent discontinue to pyrexia by 12 months with suspected and confirmed covid subjects using full analysis set.
- 4) Summary of pyrexia – Pre and post COVID period for rest of the world
- 5) Summary of pyrexia– Pre and post COVID period for Italy (Full analysis set)
- 6) Summary of pyrexia – confirmed and suspected covid subjects (Full analysis set)
- 7) Time to first pyrexia event - Pre and post COVID period for Rest of the World.

- 8) Time to first pyrexia event – Pre and post COVID period for Italy (Full analysis set).
- 9) Time to first pyrexia event – confirmed and suspected covid subjects (Full analysis set)
- 10) Kaplan-Meier plot time to first pyrexia event - Pre and post COVID period for Rest of the World.
- 11) Kaplan-Meier plot time to first pyrexia event – Pre and post COVID period for Italy (Full analysis set).
- 12) Kaplan-Meier plot time to first pyrexia event – confirmed and suspected covid subjects (Full analysis set)

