## 2 Addendum details:

The purpose of this Statistical Analysis Plan (SAP) is to outline the statistical methods and document the outputs needed for the clinical study report (CSR) of the final analysis of study CDRB436F2410, a open-label, phase IIIb study of dabrafenib in combination with trametinib in the adjuvant treatment of stage III BRAF V600 mutation-positive melanoma after complete resection to evaluate the impact on pyrexia related outcomes of an adapted pyrexia AE-management algorithm.

The final analysis was planned to be performed at the end of the study defined as 24 months after last patient last visit.

The final analysis will be a re-run of all the analyses described in the primary analysis SAP, dated on Nov 4, 2020 (/CREDI Projects/D/DRB436F/CREDI Studies/DRB436F2410/Administrative Files (study level)/RAP or RAMP Meeting - SAP\_CDRB2410\_CSR\_Primary\_Analysis\_SAP.docx

[https://webedi02.na.novartis.net:8443/webEDI02\\_non\\_SSO/drl/objectId/090095af8e1016b1](https://webedi02.na.novartis.net:8443/webEDI02_non_SSO/drl/objectId/090095af8e1016b1)).

All the analyses, data rules will follow the rules described in the above SAP. The final analysis will not include the analyses described in section 2 to support label update (Section 4.2 in the primary analysis SAP). The content of this SAP is based on protocol CDRB436F2410 version 02 (Amendment 2).

[figure not shown]
The tables/listings/figures will follow the shells described in COMBI\_Aplus\_Final reported in

/CREDI Projects/D/DRB436F/CREDI Studies/DRB436F2410/Administrative Files (study level)/RAP or RAMP Meeting - SAP\_CDRB436F2410\_COMBI\_Aplus\_Final.docx

[https://webedi02.na.novartis.net:8443/webEDI02\\_non\\_SSO/drl/objectId/090095af8b2267b8](https://webedi02.na.novartis.net:8443/webEDI02_non_SSO/drl/objectId/090095af8b2267b8)

For any occurrence , the following rules will be followed.

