#### **5.8.5 Additional analyses**

##### **Time to first occurrence**

Time to first occurrence of an event is defined as time from start of study treatment to the date of first occurrence of this event (or first event within an AE grouping), i.e. time in days is calculated as (start date of first occurrence of event) – (start of study treatment) +1.

For Kaplan-Meier analyses of time to occurrence, in the absence of an event during the on-treatment period, the censoring date applied will be **the earliest** of the following dates:

- death date
- new anticancer antineoplastic therapy start date
- end date of on-treatment period
- data cut-off date
- withdrawal of informed consent date.

Failure curves (ascending Kaplan-Meier curves) will be constructed. Median together with 95% confidence interval as well as 25th percentile and 75th percentile will be presented.

In addition, the median time to occurrence for the subset of patients who experienced the event of interest will be calculated. Simple descriptive statistics, median, min and max as well as 25th percentile and 75th percentile, will be presented.

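### SAP 7.1 splits the pyrexia outputs at the COVID date by calendar time alone, so the pooled or Rest-of-World post-COVID rate is expected to be lower even with no pandemic effect

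*SAP*

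**What the plan says.** SAP 7.1 sets the split at 1 March 2020 for the rest of the world and 23 February 2020 for Italy. For the former it states "That means March 1 will play a data-cut off role" and "The data from March 2, 2020 onwards will be considered as Post-Covid period". Under Primary endpoint, items 1 and 2 report the composite rate for each period, item 1 being worded "by 12 months for Rest of the World (Full analysis set) Pre-Covid and post-Covid-period". Items 4 and 5 do the same for pyrexia overall. Items 7, 8, 10 and 11 do so for time to first pyrexia. Items 3, 6, 9 and 12 split by COVID status and are not in question.

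Two gates apply: "The summary analyses will be performed if we have 10% total sample size in each of the categories", and "The KM plot will be performed only if we have more than 30 patients have pyrexia event in each of the categories".

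The general conventions add "Percentages will be calculated using the number of patients in the relevant population as the denominator". SAP 5.8.5 says "Time to first occurrence of an event is defined as time from start of study treatment". SAP 2 says "The tables/listings/figures will follow the shells described in" a separate document, which is not among those reviewed.

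**The concern.** The stated purpose of these outputs is to judge whether the pandemic affected the primary endpoint and overall pyrexia. A rate by 12 months needs 12 months of risk. The pre-COVID column covers most of everyone's treatment, including all or nearly all of the early months. The post-COVID column covers only the tail of treatment for those still on drug. Protocol 4.1 says pyrexia comes early in treatment. Placed side by side, the columns would show a fall that comes from less exposure and later treatment months, and this could mimic or hide a real pandemic effect. SAP 2 re-runs the primary-analysis outputs at the final analysis, apart from the label-update set, so the problem carries forward.

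**Working it through.** **Plan's own figure.** The SAP gives no number for the period outputs. Its Table 2-5 interval for 92/556 (13.6-19.9%) reproduces by Clopper-Pearson as 13.55-19.90%. A 16% 12-month rate is used below as a value close to that 16.5%.

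**Inputs.**
- Cut-off 26 September 2020, at last first visit (LPFV) plus 12 months (SAP 4 and 5.1). LPFV is therefore 26 September 2019 in calendar months, or 26 October 2019 in 28-day months (Protocol 3).
- Treatment length T: 336 days (12 × 28) or 365.25 days (SAP Time units).
- Starts: 37 by 30 November 2018 and 234 by 12 March 2019 (Protocol amendment notes), 556 by LPFV.
- Assumptions: linear accrual between these points, constant hazard, no COVID effect, no discontinuation, everyone split at 1 March (pooled data standing in for Rest of World).

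**Time on treatment at the split.** The last starter is at day 157 or 127 on 1 March, and at day 150 or 120 on 23 February.

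**One case in full (LPFV 26 October, T = 336).**
1. Starts after 12 March 2019: 556 − 234 = 322 over 228 days = 1.412 per day.
2. Anyone dosed by 31 March 2019 has finished by 1 March 2020. The remaining 209 days give 209 × 1.412 = 295 subjects, with on average 104.5 planned days after the split.
3. Share of planned time: 295.2 × 104.5 / (556 × 336) = 30,848 / 186,816 = 16.5%.
4. Hazard h = −ln(0.84)/336 = 0.000519 per day.
5. First events after the split, per remaining subject: [exp(−127h) − 0.84]/(209h) − 0.84 = 0.0962/0.1085 − 0.84 = 0.0473. Times 295.2 this is 13.9 events.
6. Pre: (0.16 × 556 − 13.9)/556 = 13.5%. Post over the FAS: 13.9/556 = 2.5%, ratio 5.4. Post over those within planned treatment: 13.9/295.2 = 4.7%, ratio 2.9.

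**All four cases** (post figures: first events / any post-split event, the latter from 1 − exp[−h(T − u)] for a subject at day u):

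| T, LPFV | Time share | In treatment | Pre | Post, FAS | Ratio | Post, in treatment | Ratio |
|---|---|---|---|---|---|---|---|
| 336, Sep | 13.9% | 291 | 13.9% | 2.1 / 2.4% | 6.6 / 5.9 | 4.0 / 4.5% | 3.5 / 3.1 |
| 336, Oct | 16.5% | 295 | 13.5% | 2.5 / 2.8% | 5.4 / 4.9 | 4.7 / 5.2% | 2.9 / 2.6 |
| 365.25, Sep | 17.4% | 342 | 13.4% | 2.6 / 2.9% | 5.1 / 4.6 | 4.3 / 4.8% | 3.1 / 2.8 |
| 365.25, Oct | 19.8% | 342 | 13.0% | 3.0 / 3.3% | 4.3 / 3.9 | 4.9 / 5.4% | 2.7 / 2.4 |

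**Sensitivity.** Accrual after 12 March 2019 was bent earlier or later, with 0 or 37% discontinuation (in COMBI-AD 63% completed dabrafenib). Ratios run from about 2.8 to 13 over the FAS and about 1.6 to 4.7 on treatment. If 50-70% of events fall in the first 84 days (assumed), they are 6.8-16.9 and 4.2-8.9.

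**Overall pyrexia (items 4, 5).** With 63% as in COMBI-AD, ratios are 3.4-9.2 over the FAS and 2.1-4.8 in treatment. These are approximate: the SAP on-treatment window runs 30 days past last dose, which raises the subjects with post-split time from 291-342 to 343-400.

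**Italy.** Accrual by country is not given. With split 23 February, LPFV 26 October and T = 336, assumed uniform starts from 1 June 2019 give an FAS ratio of 1.47. From 1 August they give 1.03 over the FAS and 0.94 among those still at risk.

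**Kaplan-Meier (63%).** The pre-COVID data cut gives 63% at 12 months, as it should. A post-COVID curve without late entry, among pyrexia-free subjects still within planned treatment, ends at 24-29%. With late entry from day 220 it gives 29.2-32.9%, against true values of 29.1-32.7%.

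**Gate.** 10% of 556 is 56. If it counts subjects, 291-342 pass (about 210-250 with 37% discontinuation) and the table is produced. If it counts events, about 12-18 composite events fail and the split disappears.

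**The case against.** These are descriptive outputs without a decision rule. The pre-COVID period is effectively a data cut and is usable. The denominator may be settled in the table shells, so it cannot be called missing from the plan. All of that stands. It does not rescue the comparison, because the pooled post-COVID rate comes out lower under either denominator.

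Three stronger readings are tempting and are not supported:
- *That the post-COVID period contains no treatment months 1-4.* LPFV is inferred from a planned cut-off that SAP 5.1 allows to move. With 28-day months the statement holds for a cut-off up to 11 October 2020 (4 October for Italy). Day 120 is 3.94 of the SAP's 30.4375-day months.
- *That the rate must also be lower in Italy.* The assumed accruals above show it need not be.
- *That a several-fold fall is certain.* The on-treatment ratio can be as low as about 1.6.

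A further objection is that finely banded rates would be sparse: about 2-3, 4-5 and 6-7 post-COVID composite events in months 7-8, 9-10 and 11-12 at constant hazard. That is true, but it reflects how little the data can say, which the percentages conceal.

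**Conclusion.** The concern holds for the pooled and Rest-of-World outputs. A calendar split without alignment to treatment time yields a lower post-COVID rate with no pandemic effect: about 4-7 times lower over the FAS and about 2-3.5 times lower among subjects still in treatment, at constant hazard and a 16% 12-month rate. The range widens down to about 1.6 under other accrual and discontinuation assumptions, and upward if events are early. It rests on the planned cut-off and on interpolated accrual. For Italy the outputs share the defect, but its direction is unknown.

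A reader might infer that the primary conclusion is at risk. It is not: the 20% test uses all on-treatment events regardless of date. This is a cheap improvement to supporting outputs.

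**What to change.** - **(a)** Keep the pre-COVID output as a data cut at the split date and compare it with the main result. Truncated follow-up alone lowers its crude rate (13.0-13.9% against 16% above), so read it beside the Kaplan-Meier estimate.
- **(b)** In items 1, 2, 4 and 5, replace the post-COVID percentages by event rates per person-time among subjects on treatment and at risk, using the SAP on-treatment window. Compare before and after the split within treatment-month bands covering all post-split months, including 5-6, or fit a treatment-time model with COVID period as a time-varying covariate. State whether first or any post-split events count. Unbanded person-time is not enough: with early events (Weibull shape 0.5, 16.5% at 12 months, 20% discontinuation) and no COVID effect it gives 22.7 against 11.2 per 100 person-years.
- **(c)** In items 7, 8, 10 and 11, let subjects enter the post-COVID risk set at their treatment day on the split date. Start the curve at a landmark with an adequate risk set, for example about day 220; at day 130 only about 4 subjects would be in it (3 days × 1.412, LPFV 26 October).
- **(d)** State whether the 10% gate counts subjects or events.

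The cost is SAP wording and modest reprogramming on data already collected. If the date-split tables were already produced at the primary analysis, the aligned versions can be added beside them to keep comparability. The downside is precision: about 8-17 post-COVID composite events pooled (12-17 without discontinuation, 8-12 with 37%), so intervals will be wide and Italy may be too sparse to report separately.
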